Main Inclusion Criteria	(1) aged 18–35, (2) identify as a gay or bisexual man, (3) HIV-negative status confirmed through in-office testing, (4) diagnosis of any Diagnostic and Statistical Manual (DSM-5) depressive, anxiety, or trauma- and stressor-related disorder; (5) HIV sexual risk (≥ 1 act in past-90-day of condomless anal sex with a male partner of unknown status or HIV+ status, unless with a HIV+ primary/main partner with known undetectable viral load); (6) not currently adherent to PrEP (pre-exposure prophylaxis) (defined as taking 4 or more days per week) (7) NYC or Miami residential stability and planned availability for 12 months; and (8) provision of informed consent.

STATISTICAL ANALYSIS PLAN

Intervention	ESTEEM is a 10-session intervention based on the Unified Protocol, an individually-delivered cognitive behavioral therapy (CBT) intervention with efficacy for reducing stress-sensitive mental health disorders (e.g., depression, anxiety) by enhancing emotion regulation skills; reducing avoidance patterns; and improving motivation and self-efficacy for behavior change. The Unified Protocol employs modules for motivation enhancement, interoceptive and situational exposure, cognitive restructuring, mindfulness, and self-monitoring techniques. Through an extensive adaptation process, we adapted the Unified Protocol to enhance young gay and bisexual men’s stigma coping by reducing minority stress processes.
Duration of Intervention	10 therapy sessions in 4 months.
Primary Outcome	The primary outcome is condomless anal sex in the absence of either PrEP or known undetectable viral load of HIV+ primary partners, measured with the Time-Line Follow-Back (TLFB), a semi-structured interview. The TLFB yields past-90-day incidence of HIV risk behavior: condomless anal sex, sex while using drugs or alcohol, number of sexual partners, and preceding-week PrEP use (i.e., coverage defined as 4+ doses per week). TLFB interviewers are masked to study arm. The primary outcome is assessed at 8-month follow-up.

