Primary Analysis	We will use a fixed sequence procedure (gatekeeper strategy) to control for multiple testing of the primary comparisons: reduction in condomless anal sex in ESTEEM vs. VCT-only and ESTEEM vs. CMHT. We will conduct the comparison of ESTEEM versus VCT-only at the 0.05 level. If we find statistical significance between ESTEEM vs. VCT-only, then we will test the second comparison ESTEEM vs. CMHT at 0.05. To make use of all data collected, we will analyze the condomless anal sex outcome using a generalized linear mixed model with a logit link using a contrast to test the comparison at the primary time point of 8 months adjusting for site.
Secondary Outcomes	Depression severity, anxiety, drug abuse, alcohol abuse, mental health diagnoses, suicidality, minority stress and universal stress processes

STATISTICAL ANALYSIS PLAN

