6.2 Sample Size Determination for the Primary Outcome

Sample size calculations were carried out using PASS 12 for logistic regression.

Our primary goal is to demonstrate a greater reduction at 8 months in condomless anal sex in the absence of either PrEP or known undetectable viral load of HIV+ primary partners, in the ESTEEM arm versus the CMHT and VCT-only arms. In our pilot study, we saw a 60% reduction in condomless anal sex at 6 months in the ESTEEM arm. We used these estimates to inform our 8-month endpoint.

Based on previous studies of VCT and the fact that CMHT does not specifically focus on condomless anal sex, we expect that these arms will yield lower reductions compared to ESTEEM, but a slightly larger reduction in CMHT (20%) compared to VCT-only (15%). To achieve at least 90% power at a 5% type I error rate, accounting for an R-square of 0.1 between treatment arm and the covariates (e.g., site, race/ethnicity), we will need 80 individuals in the ESTEEM and CMHT arms, and 40 individuals in the VCT-only arm. Although we plan to take steps to increase our retention rate from our pilot study, we conservatively estimate the retention at 8 months to be 80%. Therefore, we planned to randomize 100 ESTEEM, 100 CMHT, and 50 VCT-only young gay and bisexual men. The original target sample size was 250 participants enrolled from the two study sites [New York: 150 (60 ESTEEM, 60 CMHT, 30 VCT) and Miami: 100 (40 ESTEEM, 40 CMHT, 20 VCT)]. This was increased to 254 on 2/28/18 to correct an imbalance in the 2:2:1 randomization. The final sample size was 254.

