8.3 Analysis of Primary Outcome: HIV-Risk Behavior (Condomless Anal Sex)

8.3.1 Primary Analysis of Primary Outcome: Condomless Anal Sex

Analysis	Primary analysis of primary outcome: condomless anal sex in the absence of either PrEP or known undetectable viral load of HIV+ primary partners, measured with the TLFB, a semi-structured interview.
Analysis population	All enrolled participants
Endpoint	8-month as reported on TLFB
Unit of analysis	Participant
Method of analysis*	Generalized linear mixed model with a log (log-binomial) link using a contrast to test the comparison at the primary time point of 8 months adjusting for site and race/ethnicity (Wacholder 1986). We will conduct the comparison of ESTEEM versus VCT at 0.05 level; only if this test is statistically significant will we test ESTEEM versus CMHT at 0.05.
Handling of missing data	MAR assumption
Adjustment covariates	Study site (NYC or Miami).
Type I error	5% (2-sided)
Control of type I error	We will use a gatekeeping strategy. If the first comparison is significant at 0.05, then we will conduct the second comparison at 0.05.
Treatment effect estimate	Risk ratio with 95% confidence limits

*If the log-binomial approach fails to converge, we will use a modified log-Poisson model (Zou 2004).

Sensitivity analysis: This will only be conducted if baseline imbalance of covariates is found (see Section 7.2). Adjustment for baseline covariates not balanced at randomization.

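### The modified-Poisson fallback for the primary analysis is underspecified and, in its standard form, does not carry the missing-at-random assumption stated in the same table

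*SAP*

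**What the plan says.** **SAP 8.3.1, main model.** A generalized linear mixed model with a log (log-binomial) link, an 8-month contrast, and a risk ratio as the effect measure. The method row adjusts for site and race/ethnicity; the covariate row lists site only.

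**SAP 8.3.1, missing data.** The entry is "MAR assumption", with no method named.

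**SAP 8.3.1, fallback.** "If the log-binomial approach fails to converge, we will use a modified log-Poisson model". No working correlation, random effect, weighting or imputation is given, and failure to converge is not defined.

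**SAP 8.3.1, sensitivity analysis.** Only covariate imbalance is covered. Section 8.4.2.1 plans sensitivity analyses of the MAR assumption, but for the continuous secondary outcomes.

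**SAP Study Summary, Primary Analysis.** The same analysis has a different link: "we will analyze the condomless anal sex outcome using a generalized linear mixed model with a logit link". The stated reason is to use all the data collected.

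**SAP 6.2.** Assumed reductions are 60% (ESTEEM), 20% (CMHT) and 15% (VCT-only), with 80% retention at 8 months. No arm-level risk is stated. Eligibility requires at least one qualifying act in the past 90 days.

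**The concern.** A log link needs the linear predictor to stay below zero. A normally distributed participant effect has no upper bound, so when risks are high the model assigns some participants a probability above 1. That puts the fit under strain and makes the footnote matter.

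Modified Poisson is an estimating-equation method with robust variance, not a likelihood method. With arm-by-time terms and an independence working structure, its 8-month contrast equals a comparison of those observed at 8 months. The 4-month outcome contributes nothing, so drop-out that depends on it can bias the contrast even though such drop-out is MAR.

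The first test, ESTEEM versus VCT-only, also decides whether ESTEEM versus CMHT is tested. The 12-month binary, diagnosis and STI outcomes (8.4.1, 8.4.2.2, 8.5.1) reuse the same method.

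**Working it through.** **1. The plan's own figures, and what they imply for risk.** SAP 6.2 needs 80/80/40 evaluable: "To achieve at least 90% power at a 5% type I error rate", with R-square 0.1. The retention step reproduces: 80/0.8 = 100 and 40/0.8 = 50.

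Power was checked with a two-proportion normal approximation, two-sided 5%, each n multiplied by (1 − 0.1):

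power = Φ[(|p1 − p2| − 1.96·s0)/s1], where s0 is the pooled and s1 the unpooled standard error.

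- Baseline 100% (risks 0.40/0.80/0.85): 99.9% for both comparisons. For 90% power, 34 per arm (ESTEEM and CMHT), or 38 ESTEEM with 19 VCT, would do. So 80/80/40 meets the target but is not reproduced as a minimum.
- Baseline 70% (0.28/0.56/0.595), ESTEEM vs CMHT: n = 72 per arm, s0 = √(0.42×0.58×2/72) = 0.0823, s1 = √((0.2016 + 0.2464)/72) = 0.0789. Power = Φ[(0.28 − 0.1612)/0.0789] = 93.4%. ESTEEM vs VCT gives 89.2%.

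The stated sample size therefore fits a baseline near 70% better than the 100% that eligibility suggests. Both are carried forward.

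**2. Share of participants with modelled risk above 1.** For arm-level risk p and random-intercept SD s, set the intercept to log p − s²/2 so that the average risk is p. Then

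share = P(Z > (−log p + s²/2)/s).

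| p | s | calculation | share |
|---|---|---|---|
| 0.80 | 0.2 | (0.2231 + 0.02)/0.2 = 1.216 | 11.2% |
| 0.80 | 0.3 | (0.2231 + 0.045)/0.3 = 0.894 | 18.6% |
| 0.85 | 0.2 | (0.1625 + 0.02)/0.2 = 0.913 | 18.1% |
| 0.85 | 0.3 | (0.1625 + 0.045)/0.3 = 0.692 | 24.5% |

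The values of s are assumptions. At a 70% baseline and within-person correlation 0.3, using s² = log(1 + 0.3(1 − p)/p), the share is 7–8% in the comparators.

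**3. Does the fit fail?** Fixed-effects log-binomial models were fitted to simulated 8-month data, n = 80/80/40, with assumed covariate effects and race/ethnicity mix. Share not converged or on the boundary:

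| Baseline | Site only | Site + race/ethnicity |
|---|---|---|
| 100% | 8–16% | 52–79% |
| 80% | 0–1% | 10–36% |
| 65% | 0% | 4–15% |

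Outright non-convergence was at most 6% throughout. Most problem fits sat on the boundary and reported convergence, so the footnote as worded would not be triggered. A log-link mixed-model routine failed at every risk tried, including low ones. It therefore says nothing about these risks in particular and is not used as evidence.

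**4. Bias of the standard fallback.** Let risk be p at 4 and 8 months, within-person correlation ρ = 0.3, and drop-out d1 for those at risk at 4 months and d0 for the others. The risk among those seen at 8 months is

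[p(1 − d1)(p + ρ(1 − p)) + (1 − p)(1 − d0)·p(1 − ρ)] / [p(1 − d1) + (1 − p)(1 − d0)].

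Example, p = 0.60, d1 = 0.30, d0 = 0.10: (0.42×0.72 + 0.36×0.42)/(0.42 + 0.36) = 0.4536/0.78 = 0.582. With flat 20% drop-out the comparator stays at 0.60, so the risk ratio is 0.582/0.60 = 0.97.

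Estimated risk ratio when the true value is 1.00:

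| Drop-out pattern | p = 0.60 | p = 0.80 | p = 0.85 |
|---|---|---|---|
| ESTEEM 30%/10%, comparator flat | 0.97 | 0.98 | 0.99 |
| ESTEEM 40%/10%, comparator flat | 0.95 | 0.97 | 0.98 |
| ESTEEM 30%/10%, comparator 10%/30% | 0.94 | 0.97 | 0.98 |

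Equal dependence in both arms leaves a null ratio at exactly 1. It still moves a non-null one: with risks 0.40 and 0.85 (true 0.471), the 30%/10% pattern gives 0.382/0.840 = 0.456 and the 40%/10% pattern gives 0.372/0.832 = 0.447.

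**5. Does the form of the fallback matter?** Simulations used 100 vs 50 participants, risk 0.6 in both arms, latent correlation 0.6, and a 30-point drop-out difference by 4-month outcome in opposite directions by arm. Complete-case or independence modified Poisson gave a mean risk ratio of 1.13 and 14.1% rejections at nominal 5%. An exchangeable repeated-measures version gave 0.998 and 3.4%. The direction of the bias follows the assumed direction of drop-out.

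**The case against.** Several points on the other side stand.

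- A reader might infer that the mixed model is likely to fail, so that the fallback becomes the primary analysis. The documents do not support that. The 0.80–0.85 risks come from applying the assumed reductions to an unstated 100% baseline, the sample size points nearer 70%, and failure of the mixed model was not shown to be likely.
- A reader might also infer that the fallback cannot be valid under MAR. The SAP does not say it is a complete-case or independence fit. The footnote amends a repeated-measures model, the Summary wants all data used, and an exchangeable version removed most of the bias in step 5.
- The null bias needs drop-out to depend on the 4-month outcome differently by arm. The documents give no evidence of this. Drop-out unrelated to that outcome causes no bias.
- In step 4 the null bias is smallest at the high risks where the log link is under most strain. Total ESTEEM loss in those scenarios is 22–28% at risk 0.60 (0.6×0.30 + 0.4×0.10 = 0.22; 0.6×0.40 + 0.4×0.10 = 0.28) and higher at 0.80–0.85. The plan's 20% loss is itself called conservative.

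These points limit the size of the concern. They do not supply the missing specification: nothing in the SAP says how the fallback handles missing 8-month outcomes, and the MAR sensitivity analyses in 8.4.2.1 do not cover the primary outcome.

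**Conclusion.** The concern holds in a limited form. The fallback is underspecified and, in its standard complete-case or independence form, is inconsistent with the MAR entry in the same table. Reaching it, or accepting a boundary fit unnoticed, is a real possibility if baseline risk is near 100%, and less so at 65–80%.

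Under the assumed drop-out patterns, a null risk ratio moves to 0.94–0.97 at risk 0.60 and to 0.97–0.99 at 0.80–0.85. With equal dependence in both arms, a ratio of 0.47 moves to about 0.45. Individually these shifts are modest. In the most adverse setting simulated, the false-positive rate of a gatekeeping comparison rose to 14%.

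Baseline risk, random-intercept SD, within-person correlation, covariate effects and drop-out patterns are all assumptions. The gap in specification does not depend on them. The change should be made, but the plan is not unworkable without it.

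**What to change.** Amend 8.3.1, before outcomes are analysed by arm, as follows.

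1. Define failure of the log-binomial model to include boundary fits (any fitted risk at or numerically equal to 1) as well as non-convergence.
2. Specify a fallback that keeps all follow-up data under MAR, in one of two forms:
   - a logit-link mixed model on the 4-, 8- and 12-month data, with the 8-month risk ratio taken from predicted risks integrated over the random effect and bootstrap or delta-method limits. Predictions with the random effect set to zero would not give the population risk ratio; or
   - modified Poisson on multiply imputed data, with the 4-month outcome in the imputation model and participant-clustered variance.
3. Reconcile the logit link in the Study Summary with the log link in 8.3.1, and the two covariate lists within 8.3.1.
4. Add a missing-data sensitivity analysis for the primary outcome, as 8.4.2.1 already does for the continuous secondaries.

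If the logit model is chosen, state its estimation settings and its own failure rule. In a small check at 100% baseline, a default routine returned an error or a warning (not distinguished) in 19 of 20 simulated fits, so it should not be assumed trouble-free.

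The cost is SAP wording, a few lines of code and a little more analysis work. No new data are needed.

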8.3.2 Supportive Analysis of the Primary Outcome: Number of Condomless Anal Sex Acts

STATISTICAL ANALYSIS PLAN

Analysis	Supportive analysis of primary outcome: number of condomless anal sex acts in the absence of either PrEP or known undetectable viral load of HIV+ primary partners, measured with the TLFB, a semi-structured interview.
Analysis population	All enrolled participants
Endpoint	8-month as reported on TLFB
Unit of analysis	Participant
Method of analysis*	Generalized linear mixed model with a log link (Poisson model) using a contrast to test the comparison at the primary time point of 8 months adjusting for site and baseline number of sex acts. We will conduct the comparison of ESTEEM versus VCT at 0.05 level; only if this test is statistically significant will we test ESTEEM versus CMHT at 0.05.
Handling of missing data	MAR assumption
Adjustment covariates	A priori covariates include: study site (NYC or Miami); baseline number of sex acts
Type I error	5% (2-sided)
Control of type I error	We will use a gatekeeping strategy. If the first comparison is significant at 0.05, then we will conduct the second comparison at 0.05.
Treatment effect estimate	Risk ratio with 95% confidence limits

*We will assess for overdispersion. If there is a large amount of overdispersion, we will correct the Poisson model to take this into account. We will also assess for zero-inflation. If there are excess zeros, we will use a zero-inflated Poisson model.

8.4 Analysis of Secondary Outcomes

Secondary outcomes of interest: Condomless anal sex at 12 months (binary); Condomless anal sex at 8 and 12 months (count); Depression severity, as measured using the HAMD depression severity score, ODSIS, and BSI at 8 and 12 month time points; Anxiety, as measured by the BAI, OASIS, BSI, and SIAS at 8 and 12 month time points; Drug abuse, as measured by the

STATISTICAL ANALYSIS PLAN

SIP-D at 8 and 12 month time points; Alcohol abuse, as measured using by the AUDIT at 8 and 12 month time points; Mental health, as defined by odds of no longer having at least one *DSM-5* diagnosis (e.g., depression, anxiety) that was present at baseline still be present at 8 and 12 month time points based on the MINI (binary); Suicidality as measured by SIDAS at 8 and 12 month time points (continuous); Minority stress as captured by rejection sensitivity measured using RS, internalized homophobia measured using IHS and IAT; and sexual orientation concealment measured using SOCS at 4 and 8 month time points (continuous); Universal stress processes as captured by emotional regulation as measured by DERS, rumination as defined by RRS, assertiveness as measured by RAS, social support as measured by MSPSS, cognitive bias as measured by SRET, and impulsivity as measured by Go/No-Go at 4 and 8 month time points (continuous). Each outcome will be analyzed separately as described below.

8.4.1 Condomless anal sex at 12 months (binary and count)

These outcomes will follow the same methodology outlined above for the primary outcome.

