6.3 Power for Secondary Outcomes

For secondary outcomes (e.g., mental health, substance use), we will have 80% power to detect an effect size of 0.55 and 0.70 for ESTEEM vs. CMHT and ESTEEM vs. VCT-only, respectively, at a type I error rate of 0.01 (conservative due to multiple testing). These effect sizes are smaller than those found in the pilot ([name] et. al. 2015).

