8.4.2.1 Continuous Measures

Analysis	Mental Health and Substance Use: depression severity; anxiety; drug abuse; alcohol abuse; suicidality
Analysis population	All participants
Endpoint	Scale values at 8 and 12 months of follow-up
Unit of analysis	Participant
Method of analysis	Linear mixed model assuming missing at random (MAR)
Handling of missing data	MAR assumption
Adjustment covariates	A priori covariates include: study site (NYC or Miami); baseline score
Type I error	5% (2-sided)
Control of type I error	To control the false discovery rate, we will use the Benjamini and

STATISTICAL ANALYSIS PLAN

	Hochberg (1988) method.
Treatment effect estimate	Marginal least square mean (LSM) with 95% confidence limits if there is no treatment by time interaction ($p < 0.10$); otherwise, LSM will be summarized for each treatment and timepoint.

Sensitivity analyses will be conducted to investigate the MAR assumption, such as methods that model jointly the missingness and outcome distributions (National Research Council, 2010).

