8.4.2.2 Binary Measure

Use of the MINI to define having at least one diagnosis present at baseline, no longer present at follow-up. We will use method described above for the primary outcome and assess at 8 and 12 months.

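### Five secondary endpoints are each tested at 5% with no error control across them, because the SAP's false discovery rule covers only the continuous mental health and substance use scales

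*SAP*

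**What the plan says.** SAP 8.4.2.1 is the only part of the analysis section with a rule across outcomes. Its error-control row begins "To control the false discovery rate, we will use the Benjamini and" and continues with Hochberg, and its scope row reads "Mental Health and Substance Use: depression severity; anxiety; drug abuse; alcohol abuse; suicidality". Its stated type I error is 5%, two-sided.

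The five other endpoints are handled as follows.

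- **Condomless anal sex at 12 months, binary and count.** SAP 8.4.1: "These outcomes will follow the same methodology outlined above for the primary outcome".
- **MINI diagnosis at 8 and at 12 months.** SAP 8.4.2.2: "We will use method described above for the primary outcome and assess at 8 and 12 months".
- **Act count at 8 months.** It has its own table in SAP 8.3.2, where it is a supportive analysis of the primary outcome. Sections 4.2 and 8.4 also list it as secondary: "Condomless anal sex at 12 months (binary); Condomless anal sex at 8 and 12 months (count".

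The rule being borrowed is in 8.3.1. ESTEEM is compared with VCT-only at 0.05, and "If the first comparison is significant at 0.05, then we will conduct the second comparison at 0.05". Section 8.3.2 repeats it: "only if this test is statistically significant will we test ESTEEM versus CMHT at 0.05".

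Section 6.3 states 80% power for secondary effect sizes of 0.55 (versus CMHT) and 0.70 (versus VCT-only) "at a type I error rate of 0.01 (conservative due to multiple testing"). The protocol's account of the sample size says the same.

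**The concern.** The two-step gate was built for one outcome with two comparisons. Copied to five further endpoints, it gives each a fresh 5%. None of the five depends on the primary result, on the other four, or on the false discovery family.

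Two things follow. First, several chances of a nominally significant result remain whatever the primary test shows, and three of the five concern the primary construct. Second, closely related outcomes meet different standards. HAMD and MINI both sit under 8.4.2. HAMD is in the false discovery family, and its CMHT comparison does not depend on VCT-only. MINI is outside the family, and its CMHT comparison is reached only if the VCT-only comparison succeeds, with 40 evaluable VCT-only participants planned. The only visible reason for the difference is that MINI is binary.

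**Working it through.** **Inputs.** Five endpoints (8.3.2, 8.4.1, 8.4.2.2); 0.05 two-sided for the first step of each gate (8.3.1, 8.3.2); evaluable numbers 80, 80 and 40 (6.2). The documents give no correlations between endpoints, so those used here are assumptions.

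**The plan's own figure (6.3).** Power is approximately Φ(d/√(1/n₁+1/n₂) − 2.576) at 0.01 two-sided.

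- Versus CMHT: 0.55/√(1/80+1/80) = 3.479; 3.479 − 2.576 = 0.903; power 81.7% (80.7% with the t distribution). This reproduces the stated 80%.
- Versus VCT-only: 0.70/√(1/80+1/40) = 3.615; 3.615 − 2.576 = 1.039; power 85.1% (83.8% with t). The stated 80% is somewhat conservative.

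So 0.01 is the level behind a power figure. It is not used as a testing level anywhere in section 8.

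**At least one false ESTEEM versus VCT-only finding, all five nulls true.** If the tests are independent, the chance is 1 − (1 − α)^k.

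- Five endpoints at 0.05: 1 − 0.95⁵ = 22.6%.
- Without the 8-month count, if it is regarded only as supportive: 1 − 0.95⁴ = 18.5%.
- Five endpoints at 0.01, for comparison: 1 − 0.99⁵ = 4.9%.

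These count false differences in either direction. Counting only those in ESTEEM's favour, the first figure is 1 − 0.975⁵ = 11.9%.

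**With correlation.** One million draws of five correlated normal statistics, cut at ±1.96:

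| Assumed correlation | Chance of at least one false finding |
|---|---|
| Common 0 | 22.6% |
| Common 0.3 | 20.9% |
| Common 0.5 | 18.3% |
| 0.8 within sexual risk, 0.7 between MINI visits, 0.2 across domains | 17.1% |
| Common 0.7 | 14.9% |

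**Does the gate help?** The two-step rule was simulated with 80, 80 and 40 per arm and independent endpoints, counting a false finding on either comparison. The chance is 22.4% when all arms are equal, and 22.6% when ESTEEM truly differs from VCT-only but not from CMHT. Without the gate it is 38.7% when all arms are equal. The gate therefore keeps each endpoint near 5% over its two comparisons, but does nothing across endpoints.

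**The case against.** The strongest reply is that these are secondary outcomes. The SAP has one primary outcome with its own error rule, and how far to control error among secondaries is largely a matter of convention. The 22.6% assumes that all five nulls hold and that the tests are independent. Three of the endpoints are binary and count versions of one interview measure at two visits, so substantial correlation is plausible. The tier of the 8-month count is itself ambiguous. All of this stands. It lowers the figure and keeps the point modest. It does not explain why the SAP controls error for the scales in 8.4.2 and not for the diagnosis endpoint beside them.

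Four stronger readings are tempting, and the documents do not support them.

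- **That the five endpoints have no error control.** Each is gated across its two comparisons. What is missing is control across endpoints.
- **That 6.3 commits secondary tests to 0.01 and section 8 breaks the commitment.** 6.3 is a power statement. Planning at a stricter level than the analysis uses is conservative, and it is not a contradiction.
- **That a secondary result may rescue a failed primary.** The SAP does not say so.
- **That these five are all that lies outside the false discovery family.** The ten minority stress and universal stress measures, listed as secondary at 4 and 8 months, have only mediation models (8.4.3, 8.4.4). Table 1 also marks safe sex efficacy, decisional balance and PrEP uptake as secondary, and section 8 gives no analysis for them.

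**Conclusion.** The concern holds as a cheap improvement. False discovery control stops at the continuous scales, and five further secondary endpoints each carry their own 5% gate with nothing across them. The chance of at least one false ESTEEM versus VCT-only finding is 22.6% under independence and about 15% to 21% for common correlations of 0.7 to 0.3, given that all five nulls are true. The correlations are assumed, so the range shows the order of size and is not an estimate for this trial. The primary test and its gate are unaffected. The consequence is limited to how much weight a significant result on one of these five endpoints can bear.

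**What to change.** In 8.4.1, 8.4.2.2 and the secondary use of 8.3.2, replace the fresh 0.05 gate per endpoint. Enter the ESTEEM versus VCT-only and ESTEEM versus CMHT p-values for these endpoints, 5 × 2 = 10 in all, into the same 5% Benjamini-Hochberg family as the scales in 8.4.2.1, and list the members of that family. State the tier of the 8-month count once.

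Name the procedure without ambiguity. 8.4.2.1 dates the Benjamini and Hochberg method to 1988, but the 1988 entry in the reference list is a Bonferroni-type procedure.

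In 6.3, add a sentence saying that 0.01 was a conservative planning level and that the analysis uses false discovery control at 5%. State the multiplicity status of the ten stress measures and the three Table 1 outcomes as well.

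The cost is SAP wording and slightly lower power for the five endpoints. The loss is smallest when several scales also respond, because the Benjamini-Hochberg threshold then moves towards 5%. The VCT-first order is given up for these endpoints, so their CMHT comparison no longer depends on the small arm. False discovery control limits the expected share of false findings; it does not hold the chance of any false finding at 5% once some effects are real. If the sponsor prefers to keep the gates, the alternative is to state that these endpoints are not controlled across outcomes and to report them as exploratory.
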